#### **Clinical Hepatitis**

Subjects taking the study drugs should be monitored for the development of signs and symptoms of hepatitis which include fatigue, malaise, anorexia, nausea, dark urine and clay-colored stools, bilirubinuria, jaundice, liver tenderness, or hepatomegaly, with or without initially abnormal serum transaminase levels.

Subjects with these signs and symptoms must seek medical attention immediately and have hepatic parameters assessed. Relevant markers of viral hepatitis should also be assessed.

Subjects reporting AST/ALT elevations or clinical hepatitis should be followed until resolution of the AE or toxicity and necessary standard management should be undertaken.

### **9.7. Biomarker Evaluations**

At the time points specified in the [TIME AND EVENTS SCHEDULE](#), a blood sample will be collected for exploratory analyses of biomarkers (host RNA). In addition, leftovers from MT nasal swabs or blood samples may be used for other biomarker analyses (eg, proteins including cytokines).

Samples can only be used for research related to safety, PK and efficacy of the influenza treatment, or influenza disease. They may also be used to develop tests/assays related to influenza treatment, or influenza disease.

Analyses of biomarkers may be conducted at the sponsor's discretion and may be reported separately from this study.

### **9.8. Pharmacogenomics Evaluations**

A pharmacogenomic blood sample may be collected for future exploratory pharmacogenomic analyses (where local regulations permit). This pharmacogenomic sample collection is optional.

The sample will be collected only from subjects who consent separately to this component of the study.

Pharmacogenomic samples will be analyzed if it is hypothesized that this may help understand the clinical outcomes.

Pharmacogenomic samples may be used for research related to pimodivir or influenza A. They may also be used to develop tests/assays related to pimodivir or influenza A. Pharmacogenomic research may consist of the analysis of one or more candidate genes or of the analysis of genetic markers throughout the genome or analysis of the entire genome (as appropriate) in relation to pimodivir clinical endpoints.

### **9.9. Sample Collection and Handling**

The actual dates and times of sample collection must be recorded in the eCRF or laboratory requisition form. If blood samples are collected via an indwelling cannula, an appropriate amount (1 mL) of serosanguineous fluid slightly greater than the dead space volume of the lock will be removed from the cannula and discarded before each blood sample is taken. After blood sample collection, the cannula will be flushed with 0.9% sodium chloride, United States Pharmacopeia (USP) (or equivalent) sodium heparin of 10 U/mL and charged with a volume equal to the dead space volume of the lock.

Refer to the [TIME AND EVENTS SCHEDULE](#) for the timing and frequency of all sample collections.

Instructions for the collection, handling, storage, and shipment of samples are found in the laboratory manual that will be provided. Collection, handling, storage, and shipment of samples must be under the specified, and where applicable, controlled temperature conditions as indicated in the laboratory manual.

## **10. SUBJECT COMPLETION/DISCONTINUATION OF STUDY TREATMENT/ WITHDRAWAL FROM THE STUDY**

### **10.1. Completion**

A subject will be considered to have completed the study if he or she has completed treatment and has completed assessments at the Safety Follow-up Visit/Final Study Visit (Day 28).

### **10.2. Discontinuation of Study Treatment**

If a subject's study treatment must be discontinued before the end of the treatment regimen, this will not result in automatic withdrawal of the subject from the study.

A subject's study treatment must be discontinued if:

- The investigator believes that for safety reasons or tolerability reasons (eg, AE) it is in the best interest of the subject to discontinue study treatment.
- The subject becomes pregnant.

- The subject experiences any of the following laboratory abnormalities:
  - If baseline AST or ALT within normal range: enzyme activity increases >10x ULN
  - If baseline AST or ALT not within normal range: enzyme activity increases >10x baseline or >500 U/L (whichever occurs first)
  - Total bilirubin increases >5x ULN
  - ALT or AST >3x ULN and total bilirubin >2x ULN

If a subject prematurely discontinues study drug treatment, the subject will be asked to continue with their remaining study visits and assessment schedule. Subjects who withdraw consent during the treatment phase, will be offered an optional Safety Follow-up Visit. The optional Safety Follow-up Visit will occur the day of consent withdrawal or the day after and will consist of the same assessments as at the Final Study Visit (Day 28), with optional PRO completion.

### **10.3. Withdrawal From the Study**

A subject will be automatically withdrawn from the study for any of the following reasons:

- Lost to follow-up.
- Withdrawal of consent/assent.
- Death.

If a subject is lost to follow-up, every reasonable effort must be made by the study site personnel to contact the subject and determine the reason for discontinuation/withdrawal. The measures taken to follow up must be documented.

When a subject withdraws before completing the study, the reason for withdrawal is to be documented in the eCRF and in the source document. Study drug assigned to the withdrawn subject may not be assigned to another subject. No additional subjects will be enrolled for subjects who withdraw early. If a subject withdraws from the study before the end of the treatment or the follow-up phase, he or she will be offered an optional Safety Follow-up Visit. The optional Safety Follow-up Visit will occur on the day of withdrawal or the day after and will consist of the same assessments as at the Final Study Visit (Day 28), with optional PRO completion.

### **10.4. Withdrawal From the Use of Research Samples**

A subject who withdraws from the study will have the following options regarding the optional pharmacogenomics sample:

- The collected sample will be retained and used in accordance with the subject's original separate ICF/assent form for optional research samples.
- The subject may withdraw consent/assent for optional pharmacogenomics sample, in which case the sample will be destroyed and no further testing will take place. To initiate the sample destruction process, the investigator must notify the sponsor study site contact of withdrawal of consent/assent for the optional pharmacogenomics samples and to request

sample destruction. The sponsor study site contact will, in turn, contact the biomarker representative to execute sample destruction. If requested, the investigator will receive written confirmation from the sponsor that the samples have been destroyed.

### **Withdrawal From the Use of Samples in Future Research**

The subject may withdraw consent/assent for use of samples for research (refer to Section 16.2.5, Long-Term Retention of Samples for Additional Future Research). In such a case, samples will be destroyed after they are no longer needed for the clinical study. Details of the sample retention for research are presented in the main ICF/assent form.

## **11. STATISTICAL METHODS**

Statistical analysis will be done by the sponsor or under the authority of the sponsor. A general description of the statistical methods to be used to analyze the efficacy, PK and safety data is outlined below. Specific details will be provided in the Statistical Analysis Plan.

The primary analysis will be performed when all randomized subjects have completed the final study visit or discontinued earlier.

### **11.1. Analysis Sets**

The efficacy endpoints will be analyzed on the Intent-to-Treat-infected (ITT-i) set, consisting of all subjects who were randomized, treated and had a confirmed influenza A infection, and will be analyzed by treatment arm as randomized.

The primary endpoint will also be analyzed on the Per Protocol set, consisting of all subjects in the ITT-i set without major protocol deviations that have an effect on efficacy and who were not prematurely unblinded during the study.

All safety endpoints will be evaluated on the Safety population, consisting of all subjects who received at least one dose of study drug and will be analyzed by treatment arm as treated.

Pharmacokinetic data will be evaluated on subjects in the ITT-i set who received pimodivir. Subjects will be excluded from the population PK analysis if their data do not allow for accurate assessment of the PK parameters (eg, incomplete administration of the study drug; missing information of dosing and sampling times).

### **11.2. Subject Information**

For all subjects who receive at least 1 dose of study drug descriptive statistics will be provided. All demographic characteristics (eg, age, race, ethnicity [if allowed per local regulations], height, body weight, body mass index) and other initial subject characteristics (eg, physical examination, medical and surgical history, concomitant diseases) will be tabulated and analyzed descriptively or listed.

### **11.3. Sample Size Determination**

The study will aim to enroll 720 subjects, with 360 subjects per treatment arm.

The sample size is based on the primary endpoint of time to resolution of influenza-related symptoms. Time to resolution of influenza-related symptoms, ie, the proposed primary endpoint, will be based on the subjects' ratings on 7 items from the symptoms domain of the Flu-iiQ™ (cough, sore throat, headache, nasal congestion, feeling feverish, body aches and pains, and fatigue).

For the sample size, it is assumed that the recovery time is distributed similar to the time of symptom recovery in uncomplicated influenza, albeit with a somewhat longer average time to recovery due to the increased risk for complications and the increased time to recover for this population.

An underlying log-logistic distribution of the recovery time is assumed with a scale parameter of 0.55 and an intercept of 5.0 (in hours). Using the Gehan-Wilcoxon test to analyze the data and based on the assumption that the time to recovery is improved with 25%, a sample size of 600 subjects (randomized 1:1) will have an estimated power of 90% as based on 10,000 simulations. It is expected that approximately 15% of the total enrolled subjects may not be centrally-confirmed influenza A positive, resulting in a total of 720 subjects to be enrolled.

The effect of different distributional assumptions has been assessed, using estimates of the intercept and scale parameter from the accelerated failure time (AFT) model of time to resolution of influenza symptoms for both the log-logistic and log-normal distributions, based on data from the pimodivir Phase 2 Study 63623872FLZ2001. These estimates are provided in [Table 2](#). The scale parameter is a measure for variability of the recovery times. The intercept is a constant that cancels out in effect size estimation/simulations.

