**Table 2: Estimates of Intercept and Scale Parameter From Study 63623872FLZ2001**

Model	Parameter	Estimate	95% CI
Log-logistic	Intercept	3.8546	(3.2000, 4.5092)
	Scale	0.5213	(0.4633, 0.5867)
Log-normal	Intercept	3.6277	(2.8897, 4.3656)
	Scale	0.9880	(0.8919, 1.0945)

For a trial with a sample size of 600 patients, recovery times were simulated based on the log-logistic model and separately also based on the log-normal distribution, assuming that the time to recovery is reduced by 25% in the pimodivir with SOC treatment arm compared to the placebo with SOC treatment arm, and that the subjects are randomized in a 1:1 ratio between the 2 treatment groups. To consider the variability in the intercept and scale parameters, the simulated recovery times were derived using the estimate of each parameter and using the upper limit of the 95% CI for each parameter. A trial was simulated 10,000 times.

The Gehan-Wilcoxon test, log-logistic AFT model, and log-normal AFT model were used to analyze each of the 10,000 simulated datasets, for each recovery time distribution (log-logistic, log-normal) and for each parameter estimate (estimate, upper limit of the 95% CI). The power, for each statistical test, was estimated as the number of datasets where the 1-sided p-value from the test was <0.025 out of the 10,000 simulated datasets.

**Table 3** provides the estimates of power for each statistical test and simulated time to resolution of influenza symptoms distributions.

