**Table 3: Estimated Power From 3 Statistical Tests**

Simulated Distribution of Recovery Time	Estimated Power (%)		
	Gehan-Wilcoxon	AFT Log-logistic Model	AFT Log-normal Model
Log-logistic (estimate)	97.3	97.3	96.2
Log-logistic (upper CL)	93.3	93.4	91.3
Log-normal (estimate)	93.7	94.2	94.8
Log-normal (upper CL)	88.3	89.1	89.6

For the simulated recovery times based on the log-logistic model, the estimated power was greater than 90% when using both the estimate and the upper limit of the 95% CI for the intercept and scale parameter from the Phase 2 study.

For the simulated recovery times based on the log-normal model, the estimated power was greater than 90% and greater than 85% when using the estimate and the upper limit of the 95% CI, respectively, for the intercept and scale parameters from the Phase 2 study.

The sample size considerations are not based on accrual time and estimates of median survival times because all patients will have the same follow-up time by study design (28 days) and censoring is independent from time point of enrollment in the study, making accrual time not a concern. Also, the treatment effect is expressed as a 25% improvement (reduction) in time to resolution of influenza symptoms, and therefore does not require median times for sample size and power calculations.

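### The stated inputs give about 96% power at 600 subjects, not 90%, and the plan's own power table rules out 90% for that case

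*Protocol*

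**What the plan says.** Protocol 11.3 assumes log-logistic recovery times (scale 0.55, intercept 5.0 on the log-hour scale), a 25% improvement in recovery time and the Gehan-Wilcoxon test. It concludes that "a sample size of 600 subjects (randomized 1:1) will have an estimated power of 90% as based on 10,000 simulations". The same sentence stands in the Protocol synopsis (Sample Size Calculation) and in SAP 1.4.

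The effect is defined at the end of Protocol 11.3: "the treatment effect is expressed as a 25% improvement (reduction) in time to resolution of influenza symptoms". On the intercept the section says: "The intercept is a constant that cancels out in effect size estimation/simulations".

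The section then reports a second set of simulations for 600 subjects, again 1:1, with a 25% reduction and 10,000 runs. These use Phase 2 estimates from Protocol Table 2, where the log-logistic scale is 0.5213 with 95% confidence limits "0.4633, 0.5867". Power is "the number of datasets where the 1-sided p-value from the test was <0.025 out of the 10,000 simulated datasets". The Gehan-Wilcoxon column of Protocol Table 3 gives 97.3% at the log-logistic estimate and 93.3% at the upper limit. The text below it says that for log-logistic times "the estimated power was greater than 90% when using both the estimate and the upper limit of the 95% CI". SAP 1.4 repeats both tables as its Tables 1 and 2.

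**The concern.** The headline sentence and the log-logistic rows of Table 3 share the distribution, the test, the effect, the sample size and the number of runs. They differ only in the scale and in the intercept, which the plan says does not matter. Power falls as the scale rises, and 0.55 lies between 0.5213 and 0.5867. On the plan's own figures, power at 0.55 must therefore lie between 93.3% and 97.3%. The sentence says 90%.

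This sentence is the stated basis for 600 evaluable subjects. If its inputs do not produce its result, a reader cannot tell whether the power, the scale, the effect or an unstated setting is wrong.

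**Working it through.** **Inputs**

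- 600 subjects, 1:1, so 300 per arm (Protocol 11.3).
- Log-logistic times, scale s = 0.55, intercept 5.0 (Protocol 11.3).
- 25% reduction, so time ratio 0.75 and |ln 0.75| = 0.2877 (Protocol 11.3).
- One-sided 0.025. This is stated for the Table 3 simulations and agrees with the two-sided 5% test in Protocol 11.4. Applying it to the headline sentence is an inference.
- Follow-up of 28 days, or 672 hours (Protocol 11.3).

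**Formula.** Without censoring, the large-sample power of the Wilcoxon test for a shift on the log-time scale is:

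- log-logistic: Φ(0.2877 / (s·√(12/N)) − 1.96)
- log-normal: Φ(0.2877·√(N/4)·√(3/π) / σ − 1.96)

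**Step 1: reproduce Protocol Table 3 (Gehan-Wilcoxon column, N = 600).** With √(12/600) = 0.1414, √(600/4) = 12.247 and √(3/π) = 0.9772:

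| Row | Scale | Formula | Simulated, 10,000 runs | Plan |
|---|---|---|---|---|
| Log-logistic, estimate | 0.5213 | Φ(3.902 − 1.96) = 97.4% | 97.1% | 97.3% |
| Log-logistic, upper limit | 0.5867 | Φ(3.467 − 1.96) = 93.4% | 93.1% | 93.3% |
| Log-normal, estimate | 0.9880 | Φ(3.485 − 1.96) = 93.6% | 93.6% | 93.7% |
| Log-normal, upper limit | 1.0945 | Φ(3.146 − 1.96) = 88.2% | 87.9% | 88.3% |

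All four rows agree within half a point, so the method matches the one behind Table 3.

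**Step 2: the headline case (s = 0.55).** 0.2877 / (0.55 × 0.1414) = 3.699, and Φ(3.699 − 1.96) = 95.9%. Simulation with intercept 5.0 gives 95.9% with censoring at 672 hours and 96.1% without. Repeat runs ranged from 95.6% to 96.1%. The one-sided rejection rate under no effect was 2.4%.

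**Step 3: could it be simulation noise?** With 10,000 runs the standard error is √(0.90 × 0.10 / 10,000) = 0.3 points at 90% and √(0.959 × 0.041 / 10,000) = 0.2 points at 95.9%. The gap is 95.9 − 90 = 5.9 points.

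**Step 4: what would give 90%?** The required shift is 1.96 + 1.2816 = 3.2416 standard errors. Changing one input at a time:

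- Scale: 0.2877 / (0.1414 × 3.2416) = 0.628. Simulation gives 90.1% at 0.625 and 89.5% at 0.63. This is above the Phase 2 upper limit of 0.5867.
- Effect at s = 0.55: ln ratio = 3.2416 × 0.55 × 0.1414 = 0.252, so ratio 0.777 and a reduction of 22.3%. Simulation gives 89.9% at ratio 0.777.
- Sample size at s = 0.55 and a 25% reduction: 12 × (0.55 × 3.2416 / 0.2877)² ≈ 461, or 231 per arm (462).

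These are back-calculations; none of the three values appears in the documents.

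**Step 5: other readings of the inputs (simulated)**

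| Change | Power |
|---|---|
| 25% read as 1/1.25 (ratio 0.80) | 81% to 82% |
| One-sided 0.05 | 97.8% |
| Two-sided 0.01 | 86% |
| N = 600 × 0.85 = 510 | 92.4% |
| 10% to 30% random dropout | 95% to 96% |
| 12-hourly recording | 95.9% |
| Censoring at 14 or 10 days | about 96% |

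None comes within 2 points of 90%.

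**The case against.** The strongest reply is that the headline sentence does not list all its settings. It gives no significance level, censoring, dropout or contamination rule, so an unreported conservative setting could lie behind the 90%. Dilution would move the figure that far: if 10% of treated subjects had no benefit, power would be about 91%, and with 15% about 87%. But nothing in the documents says this was done. It also conflicts with the design: 600 is the number before the 15% allowance for unconfirmed infection, and the efficacy set contains only confirmed infections.

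A second reply is that the operating characteristics are already disclosed. Table 3 follows directly, and the synopsis closes by saying that power is at least 88% and above 90% in most scenarios. That softens the effect on a careful reader. It does not reconcile the figures, because the only Gehan-Wilcoxon entry below 90% (88.3%) is for log-normal times and the sentence specifies log-logistic. Nor does the sentence present 90% as a floor; it calls it an estimate from simulation.

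A third reply is that writing 96% assumes the scale and effect are right. That is fair. The inputs should be confirmed before the figure is replaced.

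**Conclusion.** The point holds. The stated inputs give about 96% power, so 90% understates it by about 6 percentage points and contradicts the log-logistic rows of Protocol Table 3. The result rests on a 25% reduction meaning a time ratio of 0.75, a one-sided 0.025 level and 600 confirmed-infected subjects. It is insensitive to the 28-day censoring.

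The error is conservative. On these assumptions the trial is not underpowered, and 600 evaluable and 720 enrolled need not change. Nothing visible shows an effect on Type I error, the combination test or the interim rules: the combination weights in SAP 5.1.1 use the interim sample size and 720, not the planning power. The documents do not settle whether the power or an input is the wrong figure.

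**What to change.** Retrieve the inputs of the simulation behind the headline sentence, then correct the Protocol synopsis, Protocol 11.3 and SAP 1.4 in one of two ways:

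- If scale 0.55 and the 25% reduction stand, state about 96% power at 600 subjects. It may help to add that this equals about 90% power for a reduction of about 22%.
- If 90% came from other inputs, state them and justify them, in particular any log-logistic scale above the Phase 2 upper limit of 0.5867.

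Keep 720. As a precaution only, confirm which planning power was used in the interim sample-size and futility rules, which are held in separate documents (Protocol 11.11 and SAP 3.1).

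The cost is a text correction in three places. The sample size, the tests and the conduct of the trial do not change.

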**Table 2: Estimates of Intercept and Scale Parameter From Study 63623872FLZ2001**

Model	Parameter	Estimate	95% CI
Log-logistic	Intercept	3.8546	(3.2000, 4.5092)
	Scale	0.5213	(0.4633, 0.5867)
Log-normal	Intercept	3.6277	(2.8897, 4.3656)
	Scale	0.9880	(0.8919, 1.0945)

For a trial with a sample size of 600 patients, recovery times were simulated based on the log-logistic model and separately also based on the log-normal distribution, assuming that the time to recovery is reduced by 25% in the pimodivir with SOC treatment arm compared to the placebo with SOC treatment arm, and that the subjects are randomized in a 1:1 ratio between the 2 treatment groups. To consider the variability in the intercept and scale parameters, the simulated recovery times were derived using the estimate of each parameter and using the upper limit of the 95% CI for each parameter. A trial was simulated 10,000 times.

The Gehan-Wilcoxon test, log-logistic AFT model, and log-normal AFT model were used to analyze each of the 10,000 simulated datasets, for each recovery time distribution (log-logistic, log-normal) and for each parameter estimate (estimate, upper limit of the 95% CI). The power, for each statistical test, was estimated as the number of datasets where the 1-sided p-value from the test was <0.025 out of the 10,000 simulated datasets.

**Table 3** provides the estimates of power for each statistical test and simulated time to resolution of influenza symptoms distributions.

**Table 3: Estimated Power From 3 Statistical Tests**

Simulated Distribution of Recovery Time	Estimated Power (%)		
	Gehan-Wilcoxon	AFT Log-logistic Model	AFT Log-normal Model
Log-logistic (estimate)	97.3	97.3	96.2
Log-logistic (upper CL)	93.3	93.4	91.3
Log-normal (estimate)	93.7	94.2	94.8
Log-normal (upper CL)	88.3	89.1	89.6

For the simulated recovery times based on the log-logistic model, the estimated power was greater than 90% when using both the estimate and the upper limit of the 95% CI for the intercept and scale parameter from the Phase 2 study.

For the simulated recovery times based on the log-normal model, the estimated power was greater than 90% and greater than 85% when using the estimate and the upper limit of the 95% CI, respectively, for the intercept and scale parameters from the Phase 2 study.

The sample size considerations are not based on accrual time and estimates of median survival times because all patients will have the same follow-up time by study design (28 days) and censoring is independent from time point of enrollment in the study, making accrual time not a concern. Also, the treatment effect is expressed as a 25% improvement (reduction) in time to resolution of influenza symptoms, and therefore does not require median times for sample size and power calculations.

